Two subsets of patients who agree to participate at specific investigational centers and to wear an accelerometer either on the ankle to measure TDS (n=100) or on the wrist to measure SDI (n=100) will be instructed on the proper use of these devices at the baseline visit (visit 2). The devices will be worn throughout the 12-week intervention period and will be returned to the investigational center at the final visit or upon early termination.

Brief Summary of Study Design for the Trial Registry:

This is a 12-week, multicenter, open-label study to evaluate the relationship between ABS eMDPI and CE-COPD in adult patients at least 40 years of age with exacerbation-prone COPD. The ABS eMDPI dose will be 90 mcg, 1 to 2 inhalations every 4 hours as needed, but patient dosing will not be limited to this dosing regimen. The purpose of this study is to evaluate the relationship between albuterol dosing and CE-COPD.

Method of Randomization and Blinding: This is a nonrandomized study. All patients will use the one Test IMP, the ABS eMDPI. Blinding is not applicable.

Investigational Medicinal Products: Dose, Pharmaceutical Form, Route of Administration, and Administration Rate

Test IMP: The ABS eMDPI dose will be 90 mcg, 1 to 2 inhalations every 4 hours as needed.

Reference IMP: Not applicable

Placebo IMP: Not applicable

Duration of Patient Participation and Maximal Exposure to IMP: The total duration of patient participation in the study is planned to be up to 14 weeks (a screening period of up to 2 weeks and a 12-week intervention period).

Study Duration: Approximately 9 months

End of Study: End of study is defined as the last visit of the last patient.

Plans for Treatment or Care After the Patient Has Ended Participation in the Study: No treatment is planned by the sponsor after the end of the study. Patients should be treated with standard of care after withdrawal from or termination of the study, as appropriate.

Inclusion Criteria: Patients may be enrolled in the study only if they meet all of the following criteria:

- a. The patient is male or female, 40 years of age or older, with a physician diagnosis of COPD. The diagnosis should include a history of forced expiratory volume in 1 second (FEV₁)/forced vital capacity <70% predicted and FEV₁ <80% predicted documented in the patient's chart.

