3. STUDY DESIGN

3.1. General Design

This is a 12-week, multicenter, open-label study to evaluate the relationship between as-needed usage of ABS eMDPI and CE-COPD in adult patients at least 40 years of age with exacerbation-prone COPD. ABS eMDPI is a rescue/reliever agent that includes an eModule on top of the approved PROAIR® RESPICLICK inhaler. The on-board electronics and power source are fully integrated into the inhaler and are designed to operate for the life of the inhaler without intervention. The electronic module records timestamped, pre-defined events such as cap open and inhalation parameters. The inclusion of the eModule has been shown to have no impact on the dose delivery compared with the approved product without the eModule.

The study will consist of a screening period of up to 2 weeks and a 12-week intervention period.

After providing written informed consent, patients will complete a screening visit (visit 1) to determine eligibility for the study. Patients will provide medical history (including prior medications), complete a physical examination, pregnancy test, if applicable, and review COPD exacerbation history. Eligible patients will return to the investigational center within 2 weeks for the baseline visit (visit 2). Those meeting entry criteria will be trained on the use of the eMDPI device and, upon demonstrated competency, will receive ABS eMDPI devices for use as rescue bronchodilators during the study. The screening visit and baseline visit may be combined.

Patients must use ABS eMDPI as their only rescue agent for the duration of their participation in this study and will be advised to place any current rescue pills, inhalers, or nebulizers, including SABA, short-acting muscarinic antagonists (SAMAs), or SABA/SAMA combination into storage. Patients may continue the use of other COPD and non-COPD medications as advised by their physician without changes unless deemed necessary by their physician. Patients will be managed according to routine clinical practice by their treating physician with no specific study-related instructions provided other than those on the proper use of ABS eMDPI.

Patients will be contacted by phone on a monthly basis for the collection of information about COPD exacerbations and treatments, concomitant medications, and adverse events. A review of the instructions for the use of ABS eMDPI and the procedure for replacement and return of ABS eMDPI will also occur during the monthly call.

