4.1. Patient Inclusion Criteria

Patients may be enrolled in this study only if they meet all of the following criteria:

- a. The patient is male or female, 40 years of age or older, with a physician diagnosis of COPD. The diagnosis should include a history of FEV₁/forced vital capacity <70% predicted and FEV₁ <80% predicted documented in the patient's chart.
- b. The patient is currently using a SABA reliever plus at least one of the following: long-acting beta agonist (LABA), an ICS/LABA, a long-acting muscarinic antagonist (LAMA), or a LABA/LAMA.
- c. The patient has had at least 1 episode of moderate or severe CE-COPD as described in Section [6.1.1](#) over the past 12 months before screening.
- d. The patient must be able to demonstrate appropriate use of albuterol from the ABS eMDPI.
- e. The patient is able to provide written informed consent.
- f. The patient must be willing and able to comply with study requirements as specified in the protocol, including the use of a wearable accelerometer for the subset of patients who consent to use of the device.
- g. The patient is willing to discontinue all other rescue or maintenance SABA or short-acting anti-muscarinic agents and replace them with the study-provided ABS eMDPI for the duration of the trial.

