5.1.1.1. Starting Dose and Dose Levels

The prescribed dose will be 90 mcg, 1 to 2 inhalations every 4 hours as needed. No dose escalations are planned.

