5.6. Prior and Concomitant Medication or Therapy

Any prior or concomitant medication a patient has had within 30 days before enrollment and up to the end of study will be recorded on the eCRF. Trade name and international nonproprietary name (if available), indication, dose, and start and end dates of the administered medication will

be recorded. The sponsor will encode all medication according to the World Health Organization drug dictionary.

The following medications will be prohibited during this study:

- any immunosuppressive or immunomodulatory agents including, but not limited to, methotrexate, cyclosporine, and interferon- α for 2 months prior to Visit 2
- levalbuterol during the 12-week intervention period
- other forms of albuterol MDI during the 12-week intervention period
- any rescue nebulizer (SABA, SAMA or SABA/SAMA) outside of a CE-COPD

At each investigational center visit and during monthly phone calls, the patients will be asked whether they have taken any medications (other than IMP), including over-the-counter medications, vitamins, or herbal or nutritional supplements, since the previous visit.

Concomitant medication and treatment will be recorded through visit 5.

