Inclusion Criteria: Patients may be enrolled in the study only if they meet all of the following criteria: a. The patient is male or female, 40 years of age or older, with a physician diagnosis of COPD. The diagnosis should include a history within the past 3 months of forced expiratory volume in 1 second (FEV ₁)/forced vital capacity <70% predicted and FEV ₁ <80% predicted documented in the patient's chart . g. The patient is willing to discontinue all other rescue or maintenance SABA or short-acting anti-muscarinic agents and replace them with the study-provided ABS eMDPI for the duration of the trial. h. Women of childbearing potential (not surgically sterile or ≥ 2 years postmenopausal) must have exclusively same-sex partners or use a highly effective method or acceptable method of birth control and must agree to continue the use of this method for the duration of the study and for 30 days after discontinuation of the IMP. Highly effective methods of birth control are defined as those, alone or in combination, that result in a low failure rate (ie, <1% per year) when used consistently and correctly. Highly effective methods of birth control in this study include combined (estrogen- and progestogen-containing) or progestogen-only	Inclusion Criteria: Patients may be enrolled in the study only if they meet all of the following criteria: a. The patient is male or female, 40 years of age or older, with a physician diagnosis of COPD. The diagnosis should include a history of forced expiratory volume in 1 second (FEV ₁)/forced vital capacity <70% predicted and FEV ₁ <80% predicted documented in the patient's chart. g. The patient is willing to discontinue all other rescue or maintenance SABA or short-acting anti-muscarinic agents and replace them with the study-provided ABS eMDPI for the duration of the trial. h. Women of childbearing potential (not surgically sterile or ≥ 2 years postmenopausal) must have exclusively same-sex partners or use a highly effective or acceptable method of birth control and must agree to continue the use of this method for the duration of the study and for 30 days after discontinuation of the IMP. Highly effective methods of birth control are defined as those, alone or in combination, that result in a low failure rate (ie, <1% per year) when used consistently and correctly. Highly effective methods of birth control in this study include combined (estrogen- and	Clarification added around patient's medical history. Verbiage added around acceptable method of birth control.

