7.5.2.2. Time to Clinical (COPD) Exacerbations Short-term Exacerbation Risk (7 days)

For each patient, the following 3 landmark use events will be identified:

- first time in study when had >4 inhalations per day ("low use group")
- first time in study when had >8 inhalations per day ("medium use group")
- first time in study when had >12 inhalations per day ("high use group")

A patient may be included in more than 1 landmark use group (for example, if had >12 inhalations a day any time during study, then on that time or already before he/she also had >8 and >4 a day).

For each landmark use groups, time to CE-COPD within 7 days since the landmark event will be estimated and plotted using Kaplan-Meier plot. The 3 groups will be presented in the same plot, to assess a possible 'dose-response' association, if higher use is associated with shorter time to CE-COPD.

If a CE-COPD has not occurred within 7 days, then that observation will be censored at 7 days or earlier if follow-up had completed/terminated before 7 days elapsed. Note, if CE-COPD occurred on the same date where landmark use happened, then time to CE-COPD will be calculated as 0.

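### Criterion g has the eMDPI replace maintenance as well as rescue short-acting agents, so counts read as as-needed use may include scheduled doses, and the absolute-threshold analyses do not separate these patients

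*Protocol*

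**What the plan says.** Criterion g, in the current Section 4.1 and the synopsis as well as in the amendment summary, reads "The patient is willing to discontinue all other rescue or maintenance SABA or short-acting anti-muscarinic agents and replace them with the study-provided ABS eMDPI". It names maintenance use explicitly.

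Other sections describe a narrower role:

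- Section 3.1: "Patients must use ABS eMDPI as their only rescue agent for the duration of their participation in this study". Only rescue products are listed for storage. Then: "Patients may continue the use of other COPD and non-COPD medications as advised by their physician without changes", unless the physician finds a change necessary.
- Section 5.1.1.1: "The prescribed dose will be 90 mcg, 1 to 2 inhalations every 4 hours as needed". The registry summary in the synopsis adds "but patient dosing will not be limited to this dosing regimen".
- Section 5.6 prohibits rescue nebulizers outside an exacerbation, levalbuterol, and other albuterol MDIs. Taking a prohibited medication leads to withdrawal under Section 4.3 d. The list does not mention a scheduled nebulizer or a non-nebulized short-acting anti-muscarinic.
- Section 4.1 b requires "The patient is currently using a SABA reliever plus at least one of the following" a set of long-acting options. It says nothing about scheduled short-acting use.

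On data, Section 5.6 records "Any prior or concomitant medication a patient has had within 30 days before enrollment" and up to study end, with name, indication, dose and dates. Dosing frequency is not among the listed fields. SAP 5.7 plans incidence tables of prior medication. SAP 4.1 splits summaries by exacerbation status and severity, and SAP 8 plans no sensitivity analysis.

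**The concern.** The study reads the inhaler count as a sign of need. The eModule is described as storing times and inhalation parameters, not the reason for a dose. A patient who gave up a scheduled short-acting agent could do one of three things: take the eMDPI on a schedule, take it only as needed after losing a regular drug on Day 1, or keep an agent that Section 5.6 does not prohibit. The same count means something different in each case, and nothing in the plan tells them apart.

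This matters most where a fixed number of inhalations per day defines the exposure. SAP 7.5.2.2 takes the first day in the study above 4, above 8 and above 12 inhalations, follows each patient for 7 days, and reads the three curves for a dose-response. A patient on a schedule above 4/day enters the lowest group on about Day 1, and the 7-day window that follows has no link to deterioration. The all-days analysis (SAP 7.5.2.3) also suggests fixed cut-offs. If entry regimen decides who is in a group, the curves cannot be read as a warning signal.

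**Working it through.** **The plan's own figures.** The plan gives no figure for scheduled use. Its event figures reproduce: 360 × (1.05 + 1.14)/2 × 12/52 = 360 × 1.095 × 0.2308 = 90.97, stated as 91. The Poisson 95% range is 73 to 110, as stated, and the probability of at least 70 events is 0.990. Only the mean rate of 1.095 per year is used below. It gives a background 7-day risk of 1 − exp(−1.095 × 7/365.25) = 2.1%.

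**Step 1: which thresholds can a schedule cross alone?** One to two inhalations every 4 hours is at most 6 × 1 = 6 to 6 × 2 = 12 per day.

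| Schedule | Per day | >4 | >8 | >12 |
|---|---|---|---|---|
| 1 four times daily, or 2 twice daily | 4 | no | no | no |
| 1 every 4 h, or 2 three times daily | 6 | yes | no | no |
| 2 four times daily | 8 | yes | no | no |
| 2 every 4 h | 12 | yes | yes | no |

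The regimen of 8/day is the one used in the asthma studies in Protocol 1.2.2. One added rescue dose takes it past 8, and five take it past 12.

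**Step 2: within-patient analyses.** Let S be a constant daily schedule. In SAP 7.1.2.3 the difference is (S + mean rescue use, days 1–7) − (S + mean rescue use, days 8–14), so S drops out. The same holds for the paired totals and maxima in 7.5.2.1. For the yes/no measures there, a patient on 8/day plus Poisson rescue of 1/day exceeds 8 on a given day with probability 1 − e⁻¹ = 0.632, and on at least one day of a week with probability 1 − e⁻⁷ = 0.999. Both weeks are almost always yes, so the pair is concordant. McNemar's test loses information but is not biased.

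**Step 3: landmark groups with no pre-event rise in anyone.** Assumptions, since the documents give no usage data: scheduled users take 8/day plus Poisson(1); others take Poisson(2); scheduled users are 10, 20 or 30% of patients.

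- Probability on one day: >4 is 1.00 against 0.053; >8 is 0.632 against 0.0002.
- Probability of ever crossing in 84 days: >4 is 1.00 against 0.989; >8 is 1.00 against 0.020.
- Share of scheduled users in the >8 group, w = s/(s + (1 − s) × 0.020): 85%, 93% and 96%.
- Group risk relative to as-needed patients, 1 + w(R − 1), where R is the event-rate ratio. With R = 1.5: 1.42, 1.46 and 1.48 for >8, and 1.05, 1.10 and 1.15 for >4. With R = 1.0: 1.00 throughout.

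With 400 patients the >8 group would be 400 × 0.118 = 47 (s = 10%) to 400 × 0.314 = 126 (s = 30%). Taking 2.1% as the as-needed risk and R = 1.5, that is roughly 47 × 0.021 × 1.42 = 1.4 to 126 × 0.021 × 1.48 = 3.9 events within 7 days.

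**Step 4: the opposite case.** Suppose crossing is a true signal but a share q of the landmark group are scheduled users at background risk. Observed risk = (1 − q) × true risk + q × 2.1%.

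| True 7-day risk | q = 5% | q = 10% | q = 20% | q = 30% |
|---|---|---|---|---|
| 10% | 9.6% | 9.2% | 8.4% | 7.6% |
| 15% | 14.4% | 13.7% | 12.4% | 11.1% |

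Here the distortion hides part of a real effect.

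**The case against.** The best defence is that criterion g governs. It is an entry condition covering all short-acting agents, the storage list in 3.1 can be read as part of it, and the other COPD medication that may continue is then whatever remains. Every dosing passage says as needed, so scheduled eMDPI use is an inference. Section 5.6 bans levalbuterol and other albuterol MDIs without limiting the ban to rescue use, so for those products keeping the old drug is already excluded. The study is exploratory, and the landmark plot has no test attached. High habitual use is also a legitimate risk marker, since the objective covers both pattern and amount of use. Heavy as-needed users would give the same landmark pattern, and a flag would not remove them.

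Most of this stands. It rules out several stronger readings:

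- A reader might infer that scheduled users cross all three thresholds without symptoms. That is secure only for >4, on schedules above 4/day. In the example above, 98.9% of as-needed patients also cross >4 at some time.
- A reader might infer that the main hypothesis test is biased. A constant schedule cancels there, and the +2 and +4 thresholds in SAP 7.1.2.4 are relative to the patient's own baseline. The 20% threshold does shift, to 1.6 inhalations at a baseline of 8.
- A reader might infer that a spurious dose-response is to be expected. That depends on an assumed rate ratio and prevalence.

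The defence does not settle what a patient on a scheduled short-acting agent is meant to do. The text never says so, and the prohibited list leaves a gap.

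**Conclusion.** The point holds in limited form. The current text gives the eMDPI two roles, and the plan does not identify patients for whom the count may include scheduled doses or be lowered by a retained agent. The main test and the paired continuous comparisons are largely protected, and the paired yes/no measures lose information without bias. The exposure lies in the absolute-threshold analyses, mainly SAP 7.5.2.2 and 7.5.2.3. Within the prescribed maximum, a schedule alone can cross >4 (if above 4/day) and >8 (only if above 8/day), and cannot cross >12. Added rescue doses extend this.

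Neither size nor direction can be fixed from the documents. The relative risk of 1.42 to 1.48 in the >8 group assumes 8 + 1 inhalations per day, a 10 to 30% share and a rate ratio of 1.5; at a ratio of 1.0 it is 1.00. Dilution from 10% to between 9.6% and 7.6% assumes background risk and a 5 to 30% share. Because plausible assumptions point in different directions, a gradient across the three curves, or its absence, could not be attributed to pre-event deterioration without knowing who was on a schedule. That merits a clarification and a stratified display; it does not call for a redesign.

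**What to change.** 1. Reconcile Protocol 4.1 g with 3.1, 5.1.1.1 and 5.6 on scheduled short-acting agents. This review takes no view on which rule should apply.
2. Derive a yes/no flag for scheduled SABA or short-acting anti-muscarinic use at entry from the prior-medication record. Confirm dosing frequency from source, because the fields listed in 5.6 do not assure it.
3. Present SAP 7.5.2.2 and the absolute-threshold measures in 7.5.2.1 overall and by this flag.
4. Pass the flag as a candidate baseline predictor to the separately reported predictive work (SAP 7.5.2.3 and 7.5.3). The models of Protocol 9.5.2.1 have been moved there, so a change to the protocol section alone would not reach them.

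Cost: a clarifying sentence, one derived variable with a source check, and an extra column or panel in a few outputs. Sample size does not change. The flagged subgroup may be small, in which case the split is descriptive only, but its size would at least be known.

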APPENDIX G PRODUCT COMPLAINTS		
2. Handling of Investigational Medicinal Product(s) at the Investigational Center(s) The investigator is responsible for retaining the product in question in a location separate from the investigator's clinical study supplies. The sponsor may request that the investigator return the product for further evaluation and/or analysis. If this is necessary, the clinical study monitor or designee will provide the information needed for returning the IMP. If it is determined that the investigational center must return all IMP, the sponsor will provide the information needed to handle the return. The integrity of the randomization code and corresponding blinded clinical supplies will be maintained whenever possible. A serious adverse event or the potential for a product quality problem existing	2. Handling of Investigational Medicinal Product(s) at the Investigational Center(s) The investigator is responsible for retaining the product in question in a location separate from the investigator's clinical study supplies. The sponsor may request that the investigator return the product for further evaluation and/or analysis. If this is necessary, the clinical study monitor or designee will provide the information needed for returning the IMP. If it is determined that the investigational center must return all IMP, the sponsor will provide the information needed to handle the return.	Text removed because the study does not involve randomization. All patients will use the one Test IMP, the ABS eMDPI. Blinding not applicable.

beyond the scope of the complaint may be a reason to unblind the clinical supplies for an affected patient.		
--	--	--

APPENDIX H DATA MANAGEMENT AND RECORD KEEPING

Data Collection If data are processed from other sources, these data will be sent to the investigational center, where they will be retained but not transcribed to the eCRF, unless otherwise noted in the protocol. These data may also be sent electronically to the sponsor (or organization performing data management). All patient data must have supportive original source documentation in the medical records, or equivalent, before they are transcribed to the CRF. Data may not be recorded directly on the CRF and considered as source data unless the sponsor provides written instructions specifying which data are permitted to be recorded directly to the CRF.	Data Collection If data are processed from other sources, these data will be sent to the investigational center, where they will be retained but not transcribed to the eCRF, unless otherwise noted in the protocol. These data may also be sent electronically to the sponsor (or organization performing data management).	Duplicate text deleted.
---	--	-------------------------

16.2. Amendment 02 Dated 21 March 2017

The primary reason for this amendment is a re-evaluation of the sample size needed to meet the study endpoints. This amendment is considered to be substantial (ie, it requires approval by Competent Authority, IEC, and/or IRB) by the Sponsor. All text that was removed is denoted by a strikethrough, and all added text is underlined. [Table 1](#) (Study Procedures and Assessments) has been revised to reflect changes described below. Other nonsubstantial changes have been made to the protocol (and protocol synopsis, as appropriate). These changes are unlikely to affect the safety or rights (physical or mental integrity) of the patients in this clinical study or the scientific value of the clinical study.

Changes to the Protocol

Original text with changes shown	New wording	Reason/justification for change
CLINICAL STUDY PROTOCOL SYNOPSIS (Other section affected by these changes: Section 3.2)		
Number of Investigational Centers Planned: 50 Approximately 40	Number of Investigational Centers Planned: Approximately 40	The word “approximately” was added to match text in the body of the protocol. The number of sites was also reduced.
CLINICAL STUDY PROTOCOL SYNOPSIS (Other sections affected by these changes: Section 3.2 and 9.1)		
Number of Patients Planned (Total): Approximately 600 ⁵⁰⁰ patients will be screened to achieve approximately ⁵⁰⁰ 400 enrolled patients.	Approximately 500 patients will be screened to achieve 400 enrolled patients.	The sample size was re-evaluated and adjusted to meet study endpoints. The second instance of the word “approximately” was removed from this sentence to match text in the body of the protocol.
SECTION 3.1 GENERAL DESIGN		
Those meeting entry criteria will be trained on the use of the eMDPI device and, upon demonstrated competency, will receive 3 ABS eMDPI devices for use as rescue bronchodilators during the study.	Those meeting entry criteria will be trained on the use of the eMDPI device and, upon demonstrated competency, will receive ABS eMDPI devices for use as rescue bronchodilators during the study.	The number of devices was removed from the sentence to allow for changes in the number of devices, if necessary.
SECTION 3.1 GENERAL DESIGN (Other sections affected by these changes: Section 3.5 [Table 1, footnote e], Section 5.1, and Section 5.2.3)		
Patients will receive initial eMDPI devices at visit 2 and subsequently by courier as needed, based on usage pattern, based on anticipated usage pattern. In the event that additional eMDPI devices are needed, patients will be required to visit the investigational center to receive them.	Patients will receive initial eMDPI devices at visit 2 based on anticipated usage pattern. In the event that additional eMDPI devices are needed, patients will be required to visit the investigational center to receive them.	This change was made to remove the direct-to-patient shipments. Patients will be required to visit the site for additional eMDPI devices.
SECTION 3.2 PLANNED NUMBER OF PATIENTS AND COUNTRIES (Other section affected by these changes: Section 9.1)		
The number of evaluable patients is planned to be 450 ³⁶⁰ . Details on the definition of evaluable patients and sample size are given in Section 9.	The number of evaluable patients is planned to be 360. Details on the definition of evaluable patients and sample size are given in Section 9.	The sample size was re-evaluated and adjusted to meet study endpoints.

Original text with changes shown	New wording	Reason/justification for change
SECTION 3.5 STUDY PROCEDURES AND ASSESSMENTS (TABLE 1) (Other section affected by this change: Appendix B [Sections 1, 2, and 3])		
Pre-intervention V1 Day -14 to Day 01 Intervention V2 Day 1 ±7 days Vz Up to 14 days after CE-COPD start date	Pre-intervention V1 Day -14 to Day 1 Intervention V2 Day 1 Vz Up to 14 days after CE-COPD start date	Day and allowed time windows for study visits were corrected for accuracy. Descriptive text was added to clarify the timeframe for the exacerbation visit (Vz). A sentence with similar wording was added to Appendix B, Section 3, for clarity.
SECTION 3.5 STUDY PROCEDURES AND ASSESSMENTS (TABLE 1) (Other section affected by this change: Appendix B [Section 2])		
Intervention V5 Physical examination, including height and weight X	Intervention V5 Physical examination, including height and weight X	For consistency with text elsewhere in the document, a time point was added to clarify that a physical examination will be performed at visit 5.
SECTION 4.1 INCLUSION CRITERIA		
c. The patient has had at least 1 episode of moderate or severe CE-COPD as described in Section 6.1.1 over the past 12 months before screening.	c. The patient has had at least 1 episode of moderate or severe CE-COPD as described in Section 6.1.1 over the past 12 months before screening.	Inclusion Criteria “c” was revised to include patients who experienced at least 1 episode of moderate CE-COPD in the 12 months prior to screening.

Original text with changes shown	New wording	Reason/justification for change
SECTION 4.2 EXCLUSION CRITERIA		

c. The patient has used an investigational drug within 5 half-lives of it being discontinued, or within 1 month of visit 2, whichever is longer.
 
f. The patient is known to be allergic to albuterol or any of the excipients in the IMP or rescue medication formulation (ie, lactose [milk protein]). Dietary lactose intolerance does not exclude the patient from inclusion in the study or as per the investigator's medical discretion, or lactose (milk protein).
 
h. The patient has a history or presence of "silent" infections, including of positive testing for human immunodeficiency virus types 1 and 2, hepatitis B, hepatitis C, and tuberculosis.
	
c. The patient has used an investigational drug within 5 half-lives of it being discontinued, or within 1 month of visit 2, whichever is longer.
 
f. The patient is known to be allergic to albuterol or any of the excipients in the IMP or rescue medication formulation (ie, lactose [milk protein]). Dietary lactose intolerance does not exclude the patient from inclusion in the study or as per the investigator's medical discretion.
 
h. The patient has a history of positive testing for human immunodeficiency virus types 1 and 2, hepatitis B, hepatitis C, and tuberculosis.
	
“Visit 2” was added to Exclusion Criteria “c” for clarity. Exclusion Criteria “f” was revised to include allergy to excipients of the IMP or rescue medication formulation; clarification regarding lactose intolerance was also added. Exclusion Criteria “h” was revised to reflect that testing to confirm presence of silent infections will not be performed in this study.

SECTION 6.1.1 CLINICAL EXACERBATION OF MILD, MODERATE, AND SEVERE CE-COPD		

6.1.1. Clinical Exacerbation of Mild, Moderate, and Severe CE-COPD
 
 Severe CE-COPD is defined as a CE-COPD that involves worsening respiratory symptoms for at least 2 consecutive days requiring treatment with systemic corticosteroids (at least 10 mg prednisone equivalent above baseline [Table 3]) and/or systemic antibiotics, and an unscheduled provider visit such as an office visit, urgent care visit, emergency care visit, or hospitalization. Moderate CE-COPD is defined as a CE-COPD that involves worsening respiratory symptoms for at least 2 consecutive days requiring treatment with systemic corticosteroids (at least 10 mg prednisone equivalent above baseline [Table 3]) and/or systemic antibiotics, but NOT an unscheduled provider visit such as an office visit, urgent care visit, emergency care visit, or hospitalization. Mild CE-COPD is defined as worsening of symptoms, self-managed by the patient, and does not 	
6.1.1. Clinical Exacerbation of Mild, Moderate, and Severe CE-COPD
 
 Severe CE-COPD is defined as a CE-COPD that involves worsening respiratory symptoms for at least 2 consecutive days requiring treatment with systemic corticosteroids (at least 10 mg prednisone equivalent above baseline [Table 3]) and/or systemic antibiotics, and an unscheduled provider visit such as an office visit, urgent care visit, emergency care visit, or hospitalization. Moderate CE-COPD is defined as a CE-COPD that involves worsening respiratory symptoms for at least 2 consecutive days requiring treatment with systemic corticosteroids (at least 10 mg prednisone equivalent above baseline [Table 3]) and/or systemic antibiotics, but NOT an unscheduled provider visit such as an office visit, urgent care visit, emergency care visit, or hospitalization. Mild CE-COPD is defined as worsening of symptoms, self-managed by the patient, and does not 	
The title for Section 6.1.1 was revised to include the varying levels of severity of CE-COPD. The definition of mild CE-COPD was added to this section.
 
Table 3 (Systemic Glucocorticoid Treatment Equivalent to 10 mg of Prednisone) was added to this section.

Original text with changes shown	New wording	Reason/justification for change																																																
require treatment with systemic corticosteroids or antibiotics.	require treatment with systemic corticosteroids or antibiotics.																																																	
Table 3: Systemic Glucocorticoid Treatment Equivalent to 10 mg of Prednisone	Table 3: Systemic Glucocorticoid Treatment Equivalent to 10 mg of Prednisone																																																	

  
 Glucocorticoid Treatment	Dose (mg) Equivalent to 10 mg of Prednisone	Comment	
   
 Cortisone	50	Includes parenteral	
 
 Hydrocortisone	40	Cortisol	
 
 Prednisolone	10	-	
 
 Methylprednisolone	8	Medrol: includes parenteral SOLU-MEDROL®	
 
 Triamcinolone	8	-	
 
 Betamethasone	0.4	-	
 
 Dexamethasone	0.4	Oral or parenteral DECADRON®	
  
	Glucocorticoid Treatment	Dose (mg) Equivalent to 10 mg of Prednisone	Comment	Cortisone	50	Includes parenteral	Hydrocortisone	40	Cortisol	Prednisolone	10	-	Methylprednisolone	8	Medrol: includes parenteral SOLU-MEDROL®	Triamcinolone	8	-	Betamethasone	0.4	-	Dexamethasone	0.4	Oral or parenteral DECADRON®	
  
 Glucocorticoid Treatment	Dose (mg) Equivalent to 10 mg of Prednisone	Comment	
   
 Cortisone	50	Includes parenteral	
 
 Hydrocortisone	40	Cortisol	
 
 Prednisolone	10	-	
 
 Methylprednisolone	8	Medrol: includes parenteral SOLU-MEDROL®	
 
 Triamcinolone	8	-	
 
 Betamethasone	0.4	-	
 
 Dexamethasone	0.4	Oral or parenteral DECADRON®	
  
	Glucocorticoid Treatment	Dose (mg) Equivalent to 10 mg of Prednisone	Comment	Cortisone	50	Includes parenteral	Hydrocortisone	40	Cortisol	Prednisolone	10	-	Methylprednisolone	8	Medrol: includes parenteral SOLU-MEDROL®	Triamcinolone	8	-	Betamethasone	0.4	-	Dexamethasone	0.4	Oral or parenteral DECADRON®	
Glucocorticoid Treatment	Dose (mg) Equivalent to 10 mg of Prednisone	Comment																																																
Cortisone	50	Includes parenteral																																																
Hydrocortisone	40	Cortisol																																																
Prednisolone	10	-																																																
Methylprednisolone	8	Medrol: includes parenteral SOLU-MEDROL®																																																
Triamcinolone	8	-																																																
Betamethasone	0.4	-																																																
Dexamethasone	0.4	Oral or parenteral DECADRON®																																																
Glucocorticoid Treatment	Dose (mg) Equivalent to 10 mg of Prednisone	Comment																																																
Cortisone	50	Includes parenteral																																																
Hydrocortisone	40	Cortisol																																																
Prednisolone	10	-																																																
Methylprednisolone	8	Medrol: includes parenteral SOLU-MEDROL®																																																
Triamcinolone	8	-																																																
Betamethasone	0.4	-																																																
Dexamethasone	0.4	Oral or parenteral DECADRON®																																																

Original text with changes shown	New wording	Reason/justification for change
SECTION 6.1.4 ACCELEROMETRY		

From a subset of patients who agree to participate at specific sites, SDI and TDS data will be downloaded using extraction software directly from the wearable accelerometer devices collected from the patients at their final study visit or transmitted to the central data center via Wi-Fi on a daily basis. A description of the analysis is provided in the Statistical Analysis Plan.
 
The wearable Philips accelerometer to be used in this study has been cleared by falls into a product classification that the Food and Drug Administration (FDA) has deemed through a 5010(k) exempt with intended uses consistent with those described in this study.
 
See the Study Reference ManualUser Guide for a detailed description of care and use of wearable devices.
	
From a subset of patients who agree to participate at specific sites, SDI and TDS data will be downloaded using extraction software directly from the wearable accelerometer devices collected from the patients at their final study visit. A description of the analysis is provided in the Statistical Analysis Plan.
 
The wearable Philips accelerometer falls into a product classification that the Food and Drug Administration (FDA) has deemed 510(k) exempt.
 
See the User Guide for a description of care and use of wearable devices.
	
The text was revised to reflect that accelerometer data will not be transmitted via Wi-Fi on a daily basis. The location of the description of the analysis for SDI and TDS data has been added for completeness. The product classification was updated. The location of the description of care and use of wearable devices was corrected.

SECTION 9.1 SAMPLE SIZE AND POWER CONSIDERATIONS		

Based on previous studies of an exacerbation-prone COPD cohort (Dransfield et al 2013, Vogelmeier et al 2011, Wedzicha et al 2013, Wedzicha et al 2016), it is expected that 9399 (range, 78-95 to 107-103) CE-COPD events will occur over the 12-week evaluation period in this study based on reported CE-COPD exacerbation rates of 1.05 and 1.14 events per year. Furthermore, it is the expected that 14% (14) of total exacerbations will be severe. The number of CE-COPD events requiring systemic corticosteroids is 62 (range, 43 to 82) and the expected number of severe CE COPD events is 11 (range 10 to 13).
 
This sample size (ie, n=450-400 patients, 78-95 to 107-103 CE-COPD events) is considered adequate for the fulfillment of the study objectives using univariate and multivariate analyses to evaluate the relationship of the pattern of albuterol use, inspiratory flow, SDI, and TDS data associated with the subsequent development of a moderate CE-COPD or severe CE-COPD event. Per a
	
Based on previous studies of an exacerbation-prone COPD cohort (Dransfield et al 2013, Vogelmeier et al 2011, Wedzicha et al 2013, Wedzicha et al 2016), it is expected that 99 (range, 95 to 103) CE-COPD events will occur over the 12-week evaluation period in this study based on reported CE-COPD exacerbation rates of 1.05 and 1.14 events per year. Furthermore, it is expected that 14% (14) of total exacerbations will be severe.
 
This sample size (ie, n=400 patients, 95 to 103 CE-COPD events) is considered adequate for the fulfillment of the study objectives using univariate and multivariate analyses to evaluate the relationship of the pattern of albuterol use, inspiratory flow, SDI, and TDS data associated with the subsequent development of a moderate CE-COPD or severe CE-COPD event. Per a previous study (Jenkins et al 2013), a statistically significant relationship was established between daily SABA usage and subsequent CE-COPD.
	
The sample size justification and power considerations have been revised in light of the new sample size. The duration of the evaluation period has been corrected.

Original text with changes shown	New wording	Reason/justification for change
